anticoagulation be reserved for patients with": 1) "non-valvular AF who present with a clear AF onset within 12 hours in the absence of recent stroke or transient ischemic attack (within 6 months)", and 2) "non-valvular AF and a CHADS2 score < 2 who present after 12 hours but within 48 hours of AF onset", and 3) "as an alternative to at least

3 weeks of therapeutic anticoagulation before cardioversion, TEE may be used to exclude cardiac thrombus".

As such, these recommendations will likely reduce the frequency of immediate cardioversions (in the emergency department), increase referrals for inpatient and outpatient TEEs, and increase hospital admissions. We propose a randomized control trial that will assess the utility of cardiac CT to improve patient access and timely care. The results of this study could have worldwide impact by improving patient quality of life and timely access to cardioversion.

Imaging to Rule Out LA Thrombus

Currently, TEE is considered the reference standard technique for the detection of intracardiac thrombus. Although the gold standard, a TEE-guided therapy is still associated with an embolic rate of 0.8%.⁹ TEE does have limitations which include: need for NPO x 6-8 hours, patient discomfort, potential complications associated with the procedure (infection, aspiration, perforation, bleeding, etc) or with sedation.¹⁰

Contrast enhanced ECG-gated cardiac CT (CCT) is a sensitive, noninvasive alternative method used to exclude of left atrial and LAA thrombus. CCT provides high spatial and good temporal resolution and its ability to detect thrombus has been evaluated.¹¹⁻¹⁵ CCT, compared to TEE, for the exclusion of thrombus in the LAA had a sensitivity and specificity of 100% and 99.3%, respectively (Table 1).¹⁶ A high sensitivity is needed to minimize risk of embolus, and if a thrombus is detected on CT, a confirmatory TEE may be performed or patients may receive anticoagulation. Some argue that the potential benefits of CT and its lower associated procedural risk, the risk:benefit ratio would still favour CT.

This research is novel because it will be the first to demonstrate in a RCT, that CT can be used as an alternative to TEE. More importantly, demonstrating that CT is cost-effective would be extremely attractive to all stakeholders given the growing financial burden of healthcare.

Hypothesis

- Primary Hypothesis: Compared to TEE, CCTA will:
 - 1. Reduce time to cardioversion for in-patients

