- Secondary Hypotheses: Compared to TEE, CCTA will:
 - 1. Reduce length of hospital or emergency room stay,
 - 2. Improve patient quality of life (QoL),
 - 3. Not increase adverse events (arterial embolism, procedural complications, bleeding),
 - 4. Have superior cost-effectiveness.

Study Objective

Overarching objective: To evaluate CCT as an alternative to TEE to expedite cardioversion, improve patient care and reduce hospital admissions for AF and atrial flutter.

- Primary Objective: To determine if CCT can reduce time to cardioversion for in-patients
- Secondary Objectives:
 - To determine if CCT can reduce length of stay (in-patient hospitalization and emergency department)
 - To determine if CCT improves patient QoL
 - o To determine if CCT is associated with fewer or more adverse events
 - To determine the specificity of CCT (in patients with filling defects and subsequent TEE)

Outcomes Measures

- 1. Time to cardioversion (Time from referral for imaging)
- 2. Hospital admission rate
- 3. Length of hospital stay (in-patient and emergency department stay)

- 4. QoL before cardioversion, at hospital discharge and at 30 days
- 5. Adverse events (embolic (arterial) event, procedural complication, major bleed (need definition))
 - a. Embolic arterial event
 - b. Procedural complication
 - c. All bleeding
 - d. Major bleeding
- 6. Operating characteristics (specificity, PPV) of CCT (subanalysis of patients receiving TEE after CCT)

Study Design

This randomized controlled trial will randomize patients undergoing cardioversion for AF or atrial flutter before 3 weeks of anticoagulation. This pilot (Vanguard) study will aim to demonstrate feasibility of enrolment and assist with final sample size calculation.

Inclusion Criteria

- Patients admitted to hospital or seen in the ED who require LA imaging prior to cardioversion
- Age ≥ 18 years old
- Able and willing to comply with the study procedures

Exclusion Criteria

- Indication for acute cardioversion (e.g. hemodynamic instability, acute coronary syndrome (ACS), or pulmonary edema)
- Unwillingness or inability to provide informed consent
- Contraindication to Cardiac CT
 - Severe renal insufficiency(GFR< 45ml/min)
 - Allergy to intravenous contrast agents
 - Contraindications to radiation exposure (for example, pregnancy)
 - Inability to perform 20-second breath-hold
- Contraindication to TEE
 - Unrepaired tracheoesophageal fistula
 - Esophageal obstruction or stricture

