 - Perforated hollow viscus
 - Poor airway control
 - Severe respiratory depression
 - Uncooperative, unsedated patient

Methods

Recruitment

Patients who meet the inclusion/exclusion criteria will be randomized to either the interventional arm (CCT) or standard of care (SOC) arm (TEE). Prior to randomization, written informed consent will be obtained from each patient. Patients will undergo imaging as per clinical routine and reports will be issued immediately.

TEE protocol

TEE will be performed as per clinical routine using multiple standard tomographic planes to rule-out LA/LAA thrombus. Echocardiographic analysis will include: LAA-emptying velocity, and grading the severity of LAA spontaneous ECHO. The severity of the SEC will be graded on a 4 point scale with 1 = minor homogeneous contrast enhancement, 2 = significant homogeneous contrast

enhancement, 3 = significant, dense, and inhomogeneous, slow-moving contrast, and 4 = dense slow-moving contrast.

Cardiac CT protocol

As per local protocol, a non-contrast enhanced prospective ECG-triggered image acquisition will be acquired. This will be followed by a contrast-enhanced prospective ECG-triggered will be acquired using a tri-phasic contrast protocols. Delayed CT images will be acquired 60 seconds after the initial contrast-enhanced CT scan.Cardiac CT image interpretation will be performed as per clinical routine. The LA and LAA will be assess for filling defects and characterized based upon attenuation values. If LA/LAA thrombus cannot be excluded, filling defects will be assessed on the delay images. Increases in attenuation would be consistent with pseudo-thrombus from 'slow flow' and 'incomplete opacification'. Areas where attenuation does not change significantly (persistent filling defect) will be diagnosed as thrombus. It will be recommended that patients with thrombus will undergo TEE.

Prevention of Bias

Enrolled patients will be processed through the usual clinical routine for patient booking and investigators will not influence timing of booking.

Duration of Follow-up

Patients will be followed for 30 days after cardioversion using electronic charts and telephone follow-up for QoL measures.

Sample Size Calculation

This pilot (Vanguard) study will aim to demonstrate feasibility of enrolment and assist with final sample size calculation.

Statistic Methods

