Statistical analyses will be performed using SAS and/or SPSS. Statistical significance will be defined as p<0.05. Continuous variables will be presented as means and standard deviations, and categorical variables will be presented as frequencies with percentages. To compare variables, the Wilcoxon rank sum or T-test will be used to compare continuous variables and Fisher's exact test for categorical variables. Costs will be calculated using Ontario Case Costing Initiative and the Ontario Schedule of Physician Fees and Benefits.

Randomization

Randomization will occur at time of referral for TEE and be performed using a random generator. Patients will be stratified according hospital location (CICU versus ward versus emergency department) and according to mode of cardioversion (electrical versus pharmacologic) and patient sex.

Ethical Considerations

The investigator will ensure that this study is conducted in full conformance with the principles of the "Declaration of Helsinki" or with the laws and regulations of the country in which the research is conducted, whichever affords the greater protection to the individual. The study will fully adhere to the principles outlined in "Guideline for Good Clinical Practice" ICH Tripartite Guideline or with local law if it affords greater protection to the patient. It is the responsibility of the investigator, or a person designated by the investigator to obtain signed informed consent from each patient prior to participating in this study after adequate explanation of the aims, methods, anticipated benefits, and potential hazards of the study. The investigator or designee will also explain that the patients are completely free to refuse to enter the study or to withdraw from it at any time, for any reason. If new safety information results in

significant changes in the risk/benefit assessment, the consent form will be reviewed and updated if necessary.

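### The plan does not say which test applies to time to cardioversion, and neither test it allows uses the hospital location by which patients are randomised

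*Combined protocol and SAP*

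**What the plan says.** The primary objective in the Study Objective section is "Primary Objective: To determine if CCT can reduce time to cardioversion for in-patients", and the Outcomes Measures section counts that time from referral for imaging. Length of stay is a secondary objective.

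The Statistic Methods section covers all continuous variables in one rule: "the Wilcoxon rank sum or T-test will be used to compare continuous variables". The threshold is "Statistical significance will be defined as p<0.05", with no sidedness given. The only summary is "Continuous variables will be presented as means and standard deviations".

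The Randomization section stratifies by hospital location (CICU, ward or emergency department), by mode of cardioversion and by sex. No analysis section mentions these factors. The Sample Size Calculation section gives no number, SD or effect size. It says only that "This pilot (Vanguard) study will aim to demonstrate feasibility of enrolment and assist with final sample size calculation".

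**The concern.** Two tests are permitted for the primary outcome and nothing says when each applies. They answer different questions: the t-test compares means, while the Wilcoxon test compares ranks. On the same data they can fall on opposite sides of 0.05. The plan describes no blinding of the analyst, and its Prevention of Bias section deals only with booking.

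The second gap concerns location. Stratified randomisation balances location between arms, so location adds little to the chance variation in the treatment difference. An unstratified test still counts the spread between locations as noise. Its standard error is then too large, its true size falls below 5%, and power is lost.

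At stake are the reliability of the headline p-value and the basis for the main trial, since the final sample size depends on the test and effect measure this pilot settles.

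**Working it through.** **Inputs.** From the plan: two arms, threshold 0.05, two permitted tests, three location strata. Not in the plan, so assumed: a two-sided test, 1:1 allocation, 15 to 100 per arm, CCT times 0.6 or 0.7 of TEE times, and times that are lognormal (log-SD 0.5 to 1.5), exponential or normal. The plan has no sample size or power figure to reproduce.

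**Step 1. False-positive rate** (simulation, 20,000 null trials per setting, standard error about 0.15 points).

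| How the test is chosen | Rate at nominal 5% |
|---|---|
| Wilcoxon fixed in advance | 4.4% to 5.3% |
| t-test fixed in advance | 2.6% to 5.2% |
| Chosen by a normality check | 4.4% to 5.5% |
| Both run, smaller p reported, skewed times | 5.5% to 8.3% |
| Both run, smaller p reported, normal times | 5.6% to 6.1% |

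Two independent tests would give 1 − 0.95² = 9.75%. These two share the same data, so the rate is lower.

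**Step 2. How often the choice decides the result.** P(disagree) = 2 × P(either significant) − P(t significant) − P(Wilcoxon significant). For lognormal times, log-SD 0.8, ratio 0.7:
- 30 per arm: 2 × 42.5 − 31.5 − 37.2 = 16.3%.
- 50 per arm: 2 × 62.7 − 47.7 − 57.5 = 20.2%.

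**Step 3. Which unstratified test is stronger** (simulated power, 10,000 trials per setting).

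| Setting | t-test | Wilcoxon |
|---|---|---|
| Lognormal, log-SD 0.8, ratio 0.7, 50 per arm | 47.7% | 57.5% |
| Lognormal, log-SD 1.0, ratio 0.6, 30 per arm | 34.9% | 46.8% |
| Exponential, ratio 0.7, 50 per arm | 40.6% | 32.6% |
| Exponential, ratio 0.6, 30 per arm | 46.1% | 38.2% |

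The order reverses with the shape, and the plan gives no information on shape.

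**Step 4. Effect of ignoring location.** Take lognormal times, log-SD 0.8, 50 per arm, ratio 0.7, with times multiplied by assumed location factors of 1, 1.5 and 0.6. Simulated power is 57% for the stratified Wilcoxon (van Elteren), 49% for the plain Wilcoxon and about 37% for the t-test. Under the null, stratifying restores the size from about 3% to 5%. When locations do not differ, stratifying costs almost nothing.

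A hand approximation on the log scale agrees:
- With equal thirds, the variance of the log factors (0, 0.405, −0.511) is 0.141. The share of variance within locations is 0.64 / (0.64 + 0.141) = 0.82. An unstratified test then behaves as if its critical value were 1.96 / √0.82 = 2.16, a true size of about 3.0%.
- The expected Wilcoxon z is 0.357 / (0.8 × √(2/50)) × √(3/π) = 2.18. Power is Φ(2.18 − 1.96) ≈ 59% stratified and Φ(2.18 − 2.16) ≈ 50% unstratified.

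**Step 5. In-patients only.** The primary objective concerns in-patients, so the emergency department stratum may not apply. With two equal strata at factors 1 and 1.5, the log-factor variance is (0.405/2)² = 0.041 and the within share is 0.64 / 0.681 = 0.94. The effective critical value is 2.02, the size about 4.3%, and unstratified power Φ(2.18 − 2.02) ≈ 56% against 59%. The loss is about 2 to 3 points, against about 8 with three strata.

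**The case against.** The strongest reply is that naming both tests is common shorthand for choosing by distribution. A reader might infer that the plan itself raises the false-positive rate. The documents do not support that: they do not tell the analyst to run both tests and keep the better one, and a choice by normality check stays near 5%. Skewness alone does not inflate the error either; it makes the t-test conservative.

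A reader might also infer that the t-test is simply the weaker test because times are strongly skewed. The plan never describes the distribution, and under exponential times, which are also right-skewed, the t-test has more power.

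This is a pilot aimed at feasibility, so a modest loss of size or power has limited consequence. That stands in part. The plan still states a primary efficacy hypothesis and a significance threshold, and the later sample size rests on the chosen test.

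Means are needed for the cost hypothesis and for planning, so they should not be dropped. That stands. So does the point that an ordinary Hodges-Lehmann shift does not match a stratified test. Location is only one of three stratifiers, but crossing all three gives 3 × 2 × 2 = 12 cells, about 8 patients per cell at 50 per arm (100/12), which is sparse for ranking. Finally, any test on observed times needs a stated rule for patients who are never cardioverted. That need exists whichever test is chosen.

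**Conclusion.** The concern holds in limited form. The choice of test for the primary outcome and for length of stay is open, and the analysis ignores a factor used in randomisation. The open choice can raise the false-positive rate to about 5.5% to 8%, but only if both tests are run and the smaller p-value is taken. The plan permits this without prescribing it.

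The firmer reason for a change is location. If times differ by location, both permitted tests are conservative. The Wilcoxon gives up about 8 points of power in the three-location setting and 2 to 3 points when only two in-patient strata count. If locations do not differ, there is almost nothing to gain or lose by stratifying.

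All these figures rest on assumed distributions, effects, location factors and arm sizes. The gap is modest, worth closing before data are seen, and does not invalidate the trial.

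**What to change.** In the Statistic Methods section, name one two-sided primary test for time to cardioversion: a Wilcoxon test stratified by randomised hospital location (van Elteren), using the location strata that apply to the in-patient objective. Use the same test for length of stay.

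Report medians with IQR and a location-stratified shift estimate with its 95% CI. Keep means and SDs alongside, for the cost comparison and for planning the final sample size. State in the same place how patients who are never cardioverted enter the ranking.

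The cost is a few sentences in the plan; the test is available in SAS, which the plan already names. The small downside is that the headline test becomes rank-based and no longer tests a difference in means.

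### Randomisation is stratified by location, but only unstratified tests are named: if CICU and ward differ in time to cardioversion, the in-patient comparison loses some power (efficiency, not validity)

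*Combined protocol and SAP*

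**What the plan says.** Under Randomization, the combined protocol and SAP states: "Patients will be stratified according hospital location (CICU versus ward versus emergency department) and according to mode of cardioversion" (electrical or pharmacologic), and it adds sex as a third factor. That makes 3 × 2 × 2 = 12 cells, of which 2 × 2 × 2 = 8 concern in-patients (CICU and ward).

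Under Statistic Methods the comparisons are: "the Wilcoxon rank sum or T-test will be used to compare continuous variables and Fisher's exact test for categorical variables". The planned summary is: "Continuous variables will be presented as means and standard deviations". Significance is set at p<0.05. No section names a stratified test, a regression or a covariate.

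The primary objective is: "To determine if CCT can reduce time to cardioversion for in-patients". Under Outcomes Measures, time runs from referral for imaging. The Sample Size Calculation section gives no number of patients, SD, effect or power. It says only: "This pilot (Vanguard) study will aim to demonstrate feasibility of enrolment and assist with final sample size calculation".

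**The concern.** Location was judged worth controlling at randomisation, yet the analysis then ignores it. The primary comparison spans two location strata. If CICU and ward patients wait different lengths of time, that difference adds to the spread within each arm, and an unstratified test treats it as random noise. This happens whether allocation is blocked within strata or not, so the unstated mechanics of the random generator do not decide the point.

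Two things are at stake. One is some power in the in-patient comparison. The other is what the pilot hands to the final sample size calculation: an SD not split by location mixes within-location spread with the gap between locations.

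**Working it through.** There is no stated figure to reproduce. What follows shows how the size depends on assumptions.

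**Inputs.** From the documents: alpha 0.05, in-patients in two locations, unstratified tests. Assumed: two-sided test, 1:1 allocation, 20 to 60 in-patients, 30% in CICU, lognormal times, and an observed time for every in-patient.

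**Share of variance due to location.** Let r be the ratio of ward to CICU median times and s the SD of log time within location. The variance of the location indicator is 0.3 × 0.7 = 0.21, so R² = 0.21·ln(r)² / (0.21·ln(r)² + s²).
- r = 2, s = 0.6: 0.101 / (0.101 + 0.36) = 22%
- r = 2, s = 0.9: 0.101 / (0.101 + 0.81) = 11%
- r = 1.5, s = 0.9: 0.0345 / (0.0345 + 0.81) = 4%

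**Hand check.** Leaving location out multiplies the standardised effect by about √(1 − R²). Start from 80% power (1.96 + 0.84 = 2.80):
- 22%: 2.80 × 0.883 = 2.47, power Φ(0.51) ≈ 70%
- 11%: 2.80 × 0.943 = 2.64, power Φ(0.68) ≈ 75%
- 4%: 2.80 × 0.980 = 2.74, power Φ(0.78) ≈ 78%

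This ignores the small cost of adjusting, and the help that blocking gives the unadjusted test, so it somewhat overstates the gain.

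**Simulation.** There were 10,000 replicates per setting (standard error about 0.5 point). Allocation was in blocks of 4 within location, or by simple coin-flip. The arm effect on log time was 0.444·√(60/N) at s = 0.6 and 0.666·√(60/N) at s = 0.9, so power stays in a similar range as N changes.

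| In-patients | R² | Comparison | Blocked | Simple |
|---|---|---|---|---|
| 60 | 22% | Wilcoxon v van Elteren | 69 v 77% | 67 v 76% |
| 60 | 22% | t-test v linear model (log time) | 71.7 v 80.2% | 69.5 v 79.2% |
| 60 | 11% | Wilcoxon v van Elteren | 75 v 78% | 72 v 75% |
| 60 | 11% | t-test v linear model (log time) | 76.9 v 80.4% | 74.2 v 78.1% |
| 60 | 4% | Wilcoxon v van Elteren | 77 v 78% | 76 v 76% |
| 40 | 22% | Wilcoxon v van Elteren | 68 v 76% | 65 v 74% |
| 40 | 11% | Wilcoxon v van Elteren | 73 v 76% | 72 v 75% |
| 20 | 22% | Wilcoxon v van Elteren | 64 v 72% | 60 v 66% |
| 20 | 11% | Wilcoxon v van Elteren | 69 v 71% | 66 v 66% |

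Lognormal data favour methods on log time over rank tests by construction, so the linear model is set against the t-test on log time.

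**Type I error** (20 to 60 in-patients, R² 0 to 22%). Wilcoxon: 2.7–5.0% blocked, 4.5–5.2% simple. Van Elteren: 4.4–5.4%. Linear model: 4.6–5.5%. Ignoring the strata makes the test conservative or leaves it at its nominal size.

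**Cost if location has no effect,** in points of power at 60/40/30/20 in-patients. Linear model: 0.0/0.1/0.0/0.8 blocked, 0.5/1.1/1.6/2.7 simple. Van Elteren: 0.8/1.2/1.5/3.3 blocked, 1.4/2.4/3.5/5.4 simple.

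**Check under other assumptions.** With a normal outcome, 50 in-patients, half in CICU and an effect of 0.8 SD, the unadjusted SD is √(1 + 0.25g²) for a gap of g SDs. At g = 1 this is 1.118, and analytic power is 71.6% against 80.7% adjusted. Simulation under blocking gives 71 v 79% (t-test v adjusted model) and 68 v 75% (Wilcoxon v van Elteren). At g = 0.5 the analytic figures are 78.3 v 80.7%.

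**Planning.** If the overall SD is carried into a location-adjusted final analysis, oversizing is 1/(1 − R²) − 1: 11% at R² 10% and 25% at R² 20%. The pilot's own 95% interval for the variance (df / chi-square quantiles) is 0.72–1.49 times the estimate with 60 in-patients (df 58) and 0.57–2.19 with 20 (df 18).

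**The case against.** The strongest reply is that this is a feasibility pilot with no stated sample size or power, so no promised operating characteristic is lost. That limits the weight. It does not remove the point, because the protocol states a comparative primary hypothesis and a significance level, so a test will be run.

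A second reply is that nothing in the documents says CICU and ward differ, and that choosing location as a stratification factor does not show it. This stands. With a modest location effect in a small pilot, adjustment may give nothing or lose a little. At 20 in-patients and R² 4%, a separate run gave 74.8 v 75.6% blocked and 73.8 v 72.4% simple for t-test v linear model, and 72.7 v 70.8% and 70.3 v 66.8% for Wilcoxon v van Elteren.

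Third, some in-patients may have no cardioversion time. The protocol foresees TEE or anticoagulation after thrombus on CT, and all the calculations here assume an observed time. The current tests share this gap, and a location-adjusted model does not close it. Nor do the documents say whether emergency patients who are later admitted count as in-patients.

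A reader might infer that unstratified tests after stratified randomisation give too many false positives. They do not, as the type I error figures show. A reader might also infer that the pilot will oversize the final trial. The overall SD is the right input if that trial keeps an unstratified test. Even otherwise, the 11 to 25% lies within the pilot's sampling error.

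**Conclusion.** The point holds as a conditional matter of efficiency. The plan stratifies by location and names no analysis that uses it. If location is prognostic for in-patients, power is lost that a location term would recover. With 40 to 60 in-patients the gain is about 8 to 10 points at a location R² of 22%, about 3 to 4 at 11%, and close to nil at 4%. The number of in-patients, CICU share, spread, arm effect and location effect are all assumed; none is in the documents. The plan is not invalid and contains no wrong figure here. The change is a cheap improvement, not a correction the trial depends on.

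**What to change.** In Statistic Methods:
1. For in-patient time to cardioversion, replace the open choice in "the Wilcoxon rank sum or T-test will be used to compare continuous variables" with one analysis named in advance: a linear model on log time with arm and location at randomisation (CICU v ward). Give van Elteren by location as a sensitivity analysis. Naming one analysis also removes a choice that could be made after seeing the data.
2. Do not stratify the test on all 8 in-patient cells; they would be sparse in a pilot.
3. Define in-patients by location at randomisation. Report, by arm, how many have no observed cardioversion time, since the current and the proposed analyses both need one.
4. Report the within-location SD beside the overall SD. Use the within-location SD for the final sample size only if the final analysis is also location-adjusted.

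The cost is a few sentences, since location is recorded for randomisation anyway. If location turns out not to be prognostic, the linear model gives up about 0 to 1 point of power at 40 to 60 in-patients and about 1 to 3 points near 20.
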